1.2. Endpoint(s)

This is an exploratory open-label study to evaluate potential benefits of topical application of (SSO in SAM. There is little or no historical data available on efficacy endpoints, therefore an interim analysis was planned when 100 evaluable subjects have completed the study. The results from the interim analysis will help identify key/primary efficacy endpoints. Therefore, the list of endpoints and analysis plan may be updated after the interim analysis.

The endpoints which will be investigated in the analysis are:

Primary Endpoints

• Weight gain (g/kg/day)

Secondary Endpoints

- Time (days) to discharge from acute phase
- Rate of suspected nosocomial infections (nosocomial infection will be diagnosed clinically as per hospital's management guidelines where it has been mentioned that any new sign of infection during hospital stay that was not present at admission will be considered as nosocomial infection. Following the interim analysis, the list of nosocomial infections was restricted to pneumonia, fever, UTI and sepsis.)
- Change from baseline in transepidermal water loss (TEWL) at Day 10
- Change from baseline in plasma fatty acid levels at Day 10*
- Change from baseline in c-reactive protein (CRP) at Day 10
- Change from baseline in pro-inflammatory cytokine parameters at Day 10

- Clinical improvement of visual skin condition:
 - Change from baseline in skin redness at Day 10
 - \circ Change from baseline in skin condition score at Day 10
- Change from baseline in the skin and gut microbiome data at Day 10*
- * Change from baseline in plasma fatty acid levels at day 10 will not be included in the interim analysis as the results will not be available until the end of the study. The analysis of plasma fatty acid levels will be included in the final study report. However, this analysis is outside the scope of this RAP.
- * Change in the skin and gut microbiome data will be collected for a sub-sample of subjects in the study as described in the protocol amendment. This analysis will be performed at the end of the study by an external expert at Stanford University. The metabolomic data will be analysed by the CRO (Metabolon) and additional support will be provided by the GSK subsidiary company Cellzome. As previously indicated, the analysis of skin and gut microbiome data is outside the scope of this RAP.

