9.3. Rate of suspected nosocomial infections

Derivations

Any new sign of infection during hospital stay that was not present at admission or not present for last 48 hours of hospital stay will be considered as nosocomial infection. Occurrence of the following four suspected nosocomial infections, pneumonia, fever, UTI and sepsis, is collected on the CRF. Subjects will be considered as having had a suspected nosocomial infection if they have at least one of these four infections where symptoms started during the 10-day treatment period. Pneumonia, fever, UTI and sepsis were identified during the interim results meeting as the key nosocomial infections of interest.

Summary Statistics

The number and percentage of subjects who have at least one suspected nosocomial infection during the 10 day treatment period will be summarised by treatment group. In addition the total number of infections (1, 2, 3, >3) and the type of infection will be summarised as frequency counts and percentages.

Following the interim analysis, nosocomial infections will also be summarised by age category.

Logistic Regression

The proportion of subjects who have at least one suspected nosocomial infection in each treatment group will be compared using a logistic regression. Covariates/ factors will be included in the model as described in Section 7.1Error! Reference source not found.. The odds ratio with associated 95% CI will be presented.

This analysis may not be performed if there are a low number of suspected nosocomial infections.

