10.1. Adverse Events

A listing of all new problems during the hospital stay, including nosocomial infections, will be produced.

In addition, any ongoing illnesses, as collected on the daily monitoring chart, will be listed.

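### The nosocomial infection endpoint was cut to four infections at the interim results meeting, and the any-new-infection endpoint first defined is no longer compared between arms

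*SAP*

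**What the plan says.** **The endpoint as first defined.** SAP section 1.2 lists the rate of suspected nosocomial infections as a secondary endpoint and states that "any new sign of infection during hospital stay that was not present at admission will be considered as nosocomial infection". Section 9.3 opens with a similarly broad definition.

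**The change.** Section 1.2 continues: "Following the interim analysis, the list of nosocomial infections was restricted to pneumonia, fever, UTI and sepsis". Section 9.3 gives the occasion: "Pneumonia, fever, UTI and sepsis were identified during the interim results meeting as the key nosocomial infections of interest".

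**What is now analysed.** Under section 9.3 a child has the endpoint only "if they have at least one of these four infections where symptoms started during the 10-day treatment period". The by-arm comparison uses that variable: "The proportion of subjects who have at least one suspected nosocomial infection in each treatment group will be compared using a logistic regression". An odds ratio with 95% CI is to be reported, and the model may be omitted if infections are few.

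**What is left for other infections.** Section 10.1 says: "A listing of all new problems during the hospital stay, including nosocomial infections, will be produced". No by-arm table or model of them is planned.

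**Context.** Section 1.2 begins "This is an exploratory open-label study to evaluate potential benefits of topical application of (SSO in SAM", says that the interim results will help identify the key efficacy endpoints, and allows the endpoint list to change afterwards. Section 6 deems all analyses exploratory, and section 6.2 makes no multiplicity adjustment.

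**The concern.** An event definition was narrowed at a meeting held to look at results, in a trial where allocation is not masked. The narrowed definition is then estimated in a data set that includes the children whose results were on the table. If differences between arms influenced which infections were kept, the final odds ratio carries part of the interim chance difference with it, and its confidence interval does not allow for that.

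The SAP gives the reader no means of judging whether this happened. It states no rule or reason for choosing these four and does not say whether the choice was made blind to arm. It also keeps no by-arm result for the definition that preceded the choice. Such a result could not have been affected by the selection, whatever was discussed at the meeting.

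**Working it through.** The SAP states no event rate, power or sample size for this endpoint (section 2 leaves sample size to the protocol), so there is no plan figure to reproduce. The check has two parts.

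**1. Reading the text**

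| Question | SAP | Answer |
|---|---|---|
| Was a wider definition in force before the interim? | 1.2 | Yes. The list was restricted, and the broad definition precedes it |
| When were the four chosen? | 1.2, 9.3 | After the interim, at the interim results meeting |
| Were arms compared at the interim? | 9.1 | Yes for weight gain. Not stated here for infections; the interim plan is a separate version (section 3) |
| Are the interim children in the final analysis? | 3, 4 | Yes. It covers all subjects, and nothing excludes them |
| Is the broad definition still compared by arm? | 9.3, 10.1 | No |
| Is a selection rule or reason given? | 1.2, 9.3 | No |

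Section 9.3 also summarises the type of infection, but nothing says that this goes beyond the four, so it does not restore the broad endpoint.

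**2. How large could a selection effect be?**

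A simulation under no treatment effect gives the range.

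*From the SAP:* about 100 children at the interim; four types kept; endpoint is at least one of the four; interim children included in the final test.

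*Assumed, not in the SAP:* 1:1 arms, so 50 per arm at the interim; 8 candidate types, independent, each with 6% risk; final N of 200 or 300.

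With four types at 6%, the expected composite rate is 1 − 0.94^4 = 0.219, or about 22% per arm. In each simulated trial four types are chosen from the interim children. The composite is then tested in all N children with

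z = (p_E − p_C) / sqrt[ p(1 − p) × 2/n ],

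where p_E and p_C are the composite proportions with and without emollient, n = N/2 per arm, and p is the pooled proportion. This stands in for the adjusted logistic regression. A falsely favourable result is z < −1.96 (nominal 2.5%), which is roughly an upper 95% confidence limit for the odds ratio below 1. There were 20,000 trials per setting.

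| How the four were chosen | N = 200 | N = 300 |
|---|---|---|
| Four most common types, arms pooled | 2.5% | 2.3% |
| Three fixed on clinical grounds, the fourth picked on arm difference | 5.2% | 4.8% |
| Four most favourable to emollient | about 14% | about 11% |
| As the row above, tested only in post-interim children | about 2.5% | about 2.5% |

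In the worst-case row the mean spurious difference is −5.6 percentage points at N = 200 and −3.8 at N = 300. With 6 candidate types instead of 8, the worst case at N = 200 falls to about 8%.

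A wider grid of the same worst-case rule (N from 150 to 400, 6 to 10 types, 5% or 10% risk each, 6,000 trials per setting) gave about 6% to 25%, with a median odds ratio of 0.56 to 0.91. At N = 200 with 8 types the median odds ratio was 0.70 to 0.76. Across these settings the unselected any-infection endpoint stayed at 2.0% to 3.0%.

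The result therefore depends almost entirely on the selection rule, which the SAP does not report. Both the unselected endpoint and the post-interim subset return to the nominal rate under every rule.

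**The case against.** **The choice may have been purely clinical.** Section 9.3 calls the four the key infections of interest and gives no arm-based reason. If the choice ignored arm there is no inflation, as the first row of the second table shows. This stands. A reader might infer from the results meeting and the open-label design that the odds ratio is biased, or that the list was picked to favour the oil. The SAP supports neither: it does not say that infections by arm were presented, let alone that they drove the choice.

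**The plan is exploratory and open about the change.** The endpoint is secondary, section 1.2 announced that endpoints might be updated, and the restriction is disclosed twice. This limits what a favourable result could support and lowers the weight of the point. It does not give the reader the result under the broad definition. The SAP is more careful elsewhere: when children with oedema were removed from the weight analysis after the interim, section 9.1 kept a separate summary of them.

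**The worst case is artificial.** The number of types, their rates, their independence and N are all assumed. Fever would be expected to accompany pneumonia, UTI or sepsis, so independence is doubtful. This stands; the 14% is an illustration of an extreme.

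**Effects on the dropped infections are not hidden.** A reader might suppose that skin infection was dropped and its effect lost. Section 8.3 names skin infection only as a baseline diagnosis, and nothing says that it was a recorded nosocomial type. Skin is still compared by arm through the appearance score (9.6, with a scale reaching vesicles and pustules in Supplemental Table 2), and SCORDoK is summarised by arm (9.7). What is missing is narrower: a by-arm result for any new infection.

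**The data may not support an all-type analysis.** Section 9.3 says that the four are collected on the CRF. Section 10.1 implies that other new problems are recorded, but not that they are coded as infections with onset dates. Some coding may be needed.

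**Conclusion.** The point holds as a gap in the plan; it does not show bias. The four-infection list was fixed at the interim results meeting of an open-label trial, the interim children are re-used, and the broader endpoint no longer has a by-arm analysis. The possible effect on the one-sided false-favourable rate runs from none (about 2.5%) if the choice ignored arm to about 14% in the assumed worst case at N = 200. Where the trial lies in that range cannot be told from the SAP. Because the endpoint is secondary, the study exploratory and the change disclosed, this is an improvement that should be made and no threat to the study's main conclusion. Which of the two definitions should lead is a matter of judgement; the need is for both to be shown.

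**What to change.** In section 9.3:

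1. Add the same by-arm summaries and logistic regression for any new infection not present at admission, using the new problems already recorded, beside the four-infection composite. State which wording of the broad definition applies, since 9.3 adds a 48-hour condition that 1.2 lacks.
2. Label the composite as defined after the interim. State why these four were chosen and whether infection data by arm had been seen.
3. Show the composite separately for children who completed after the interim cut. That estimate will be less precise, but the choice of infections could not have been informed by those children's results.

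*Cost:* SAP wording, one or two extra tables, and some coding of recorded new problems as infections, preferably done without knowledge of arm. The all-type endpoint is less specific than the composite, which is a reason to report the two together.

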4. ANALYSIS POPULATIONS

The following populations will be defined:

Safety population: The safety population will comprise all randomised subjects who start the SAM Routine Standard of care (with or without topical application of SSO) and will be used for the analysis of safety data. The data will be analysed according to the actual treatment received if this differs from the treatment to which the subject was randomised. If subjects receive treatment differing from that assigned by the randomisation schedule (for either a portion of or the entire time on study), they will be

analysed based on the treatment taken for the majority (>50%) of their time on study treatment.

Intent-to-Treat (ITT) population: This will consist of all randomised subjects from whom at least baseline and at least one post baseline measure have been obtained and will be used for the analysis of efficacy data. The data will be analysed according to the treatment to which the subject was randomised.

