8.3. Baseline Characteristics

Summary statistics for the weight-for-length Z (WLZ) score, length-for-age Z (LAZ) score, weight-for-age Z (WAZ) score, mid upper arm circumference, mother's / caregiver's formal years of education, father's formal years of education and duration of exclusive breast feeding at Day 0 will be summarised by treatment group for the Safety population. The number and percentage of subjects will also be presented for, presence of oedema, breast feeding history (no breast feeding since birth, partial breast feeding or exclusive breast feeding), breast feeding status (still breast feeding, not still breast feeding), type of diarrhoea and presence of pneumonia, sepsis/septicaemia, meningitis/encephalitis, vitamin A deficiency, skin infection, ileus, ASOM/CSOM, enteric fever and other clinical diagnosis and visible wasting at Day 0.

For the interim analysis only, differences between the two treatment groups (emollient therapy versus no emollient) for each baseline characteristic will be examined. For continuous data a two sample t-test will be carried out to compare the two treatment groups. If the data is not normally distributed then a non-parametric Wilcoxon rank sum test may be used instead. For categorical data a chi-squared test will be used.

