9. EXPLORATORY EFFICACY ANALYSES

All efficacy tables, listings and figures will use the ITT population unless specified otherwise.

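### The model for new infections has no term for pneumonia or sepsis already present at Day 0, and the by-type percentages include children who already have that infection

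*SAP*

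**What the plan says.** - **Event.** SAP 1.2 describes a nosocomial infection as "any new sign of infection during hospital stay that was not present at admission". Section 9.3 adds a 48-hour clause: "Any new sign of infection during hospital stay that was not present at admission or not present for last 48 hours of hospital stay". After the interim analysis the list was cut to pneumonia, fever, UTI and sepsis, and a child counts with "at least one of these four infections where symptoms started during the 10-day treatment period".
- **Summaries.** In 9.3, counts and percentages of children who "have at least one suspected nosocomial infection during the 10 day treatment period will be summarised by treatment group". Besides this composite percentage, 9.3 says that "the type of infection will be summarised as frequency counts and percentages".
- **Denominator.** Section 9.3 names no population, so the default in section 9 applies: "All efficacy tables, listings and figures will use the ITT population unless specified otherwise". Section 4 defines ITT as "all randomised subjects from whom at least baseline and at least one post baseline measure have been obtained", with no restriction on infection at Day 0.
- **Model.** The logistic row of Table 1 (section 6.1) lists treatment, sex, baseline WLZ and age.
- **Day 0 data.** Section 8.3 tabulates by arm the "presence of pneumonia, sepsis/septicaemia, meningitis/encephalitis" and other diagnoses at Day 0. Its list does not name fever or UTI.
- **Existing safeguard.** Section 6.1 has baseline differences between arms examined before the efficacy analysis. Where one is judged clinically important, an exploratory subgroup analysis is optional.

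**The concern.** A child who has pneumonia at Day 0 cannot be counted as a new pneumonia case, or can be counted only once it has cleared and returned under the 48-hour clause. The same holds for sepsis. Infection at Day 0 therefore helps to decide who can become a case. It may also mark a sicker child with a higher risk of the other listed infections.

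Section 6.1 sets out to adjust for age, sex and some baseline measure of the outcome or of severity. For this endpoint Table 1 fills that place with WLZ, a nutritional measure, and uses nothing on infection. Randomisation was stratified by age only, so Day 0 infection is balanced by chance alone.

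Two results are affected. The odds ratio can pick up a chance difference between arms in Day 0 infection. The by-type percentages divide new cases by a group that includes children who already had that infection.

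**Working it through.** The SAP gives no event rate, no Day 0 prevalence and no arm size, so there is no planned figure to reproduce. Every rate below is an assumption, and no scenario has an oil effect.

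**1. Composite odds ratio.** Let q be the share of an arm infected at Day 0, r the risk of a new infection in the other children, and m the risk ratio for children infected at Day 0.

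Arm risk = (1 − q)·r + q·m·r; OR = odds (oil) / odds (control).

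Worked case with r = 0.30 and q = 0.50 (oil) v 0.30 (control):
- m = 0.5: 0.150 + 0.075 = 0.225 v 0.210 + 0.045 = 0.255; OR = (0.225/0.775)/(0.255/0.745) = 0.85.
- m = 1.5: 0.150 + 0.225 = 0.375 v 0.210 + 0.135 = 0.345; OR = (0.375/0.625)/(0.345/0.655) = 1.14.

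Over r = 0.20 to 0.30:

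| Day 0 infection, oil v control | m = 0.5 | m = 1 | m = 1.5 |
|---|---|---|---|
| 40% v 40% | 1.00 | 1.00 | 1.00 |
| 50% v 40% | 0.92–0.93 | 1.00 | 1.06–1.07 |
| 50% v 30% | 0.85–0.86 | 1.00 | 1.12–1.14 |

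If the control arm has the excess, the ratios invert (1/0.85 = 1.18; 1/1.14 = 0.88). Within each Day 0 stratum the OR is 1.00 in every scenario.

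**2. How far m can fall through blocked components alone.** Take independent component risks for pneumonia/fever/UTI/sepsis.
- 8/10/4/4%: all four give 1 − 0.92 × 0.90 × 0.96 × 0.96 = 0.237; without pneumonia, 1 − 0.90 × 0.96 × 0.96 = 0.171. A child with Day 0 pneumonia keeps 72% of the composite risk; OR 0.96 (50% v 40%) or 0.92 (50% v 30%).
- 15/5/3/5%: 0.256 and 0.125, so 49% is kept; OR 0.92 or 0.85.
- With pneumonia and sepsis both blocked in every child infected at Day 0, the ORs run from 0.79 to 0.94.

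**3. How often an imbalance arises.** SD of the difference = √(2q(1 − q)/n). At q = 0.40 and n = 50, 100 and 200 per arm it is 0.098, 0.069 and 0.049. A difference of at least 10 points, in either direction, then has probability 31%, 15% and 4%. At least 20 points has 4% at n = 50 and 0.4% at n = 100.

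**4. By-type percentages.** Let d be the share with that infection at Day 0, r the risk of that type in children free of it, and c the relative chance that a child with it is counted again.

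Reported percentage = (1 − d)·r + d·c·r.
- Balanced arms, d = 0.40, c = 0: 60% of the risk in children who could be new cases. With c = 0.25: 0.60 + 0.10 = 70%.
- d = 0.50 v 0.40, c = 0: ratio of the arms' percentages 0.50/0.60 = 0.83. With 0.50 v 0.30: 0.50/0.70 = 0.71.

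The understatement needs no imbalance, only c below 1.

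**The case against.** The strongest case against is that the composite's at-risk set is not wrong. A child with Day 0 pneumonia can still develop fever, UTI or sepsis, and pneumonia again under the 48-hour clause, so belongs in the denominator. Balanced arms give an OR of 1.00. What remains is chance imbalance in one omitted covariate, for which the confidence interval allows across repeated trials. Sampling error is also much larger than the shift. With 15% v 16% and an assumed 100 per arm, SE(log OR) = √(1/15 + 1/85 + 1/16 + 1/84) = 0.39, so each 95% limit lies a factor of 2.15 from the estimate, against a shift of 0.93. The endpoint is secondary, all analyses are exploratory, and 6.1 already has a baseline check.

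Most of this stands for the composite and limits the weight of the point. It does not remove it. Once an imbalance is seen, the odds ratio is off by an amount that adjustment would correct, using data already collected. The 6.1 check has no threshold and leads only to an optional subgroup analysis, chosen in an open-label study after arm differences are known. The objection does not reach the by-type percentages.

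A reader might infer that leaving these children in the denominator makes the oil look protective. The documents do not support that: nothing shows which arm would have more Day 0 infection, or whether those children have a lower or higher risk of the composite. A reader might also take the extreme m = 0, where the same imbalances give ORs of 0.66 to 0.82. That would require that no child infected at Day 0 could have any listed infection, which the four-part definition in 9.3 contradicts.

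**Conclusion.** The point holds at modest weight. For the composite the gap is an omitted prognostic factor, which leaves chance imbalance and some lost precision rather than systematic bias. Its size is an OR of about 0.85 to 1.14 with no true effect, given 10 to 20 points more Day 0 infection in the oil arm, relative risks of 0.5 to 1.5 and a 20–30% risk in uninfected children. It reaches 0.79 only if pneumonia and sepsis are both blocked in every child infected at Day 0. The direction cannot be known in advance.

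The by-type percentages are the firmer part. For pneumonia and sepsis they understate the risk among children who could be new cases even with balanced arms, provided that children who already have the infection are less likely to be counted as new cases.

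**What to change.** - **Table 1, logistic row:** add one prespecified factor, pneumonia or sepsis present at Day 0 (yes/no). State that it stays in whatever its p-value, since 6.1 allows non-significant terms to be dropped. Fever and UTI are left out because the Day 0 list in 8.3 does not name them.
- **Section 9.3, by type:** keep the all-ITT summary, so that infections that clear and return under the 48-hour clause are still shown. Add, for pneumonia and for sepsis, the percentage among children free of that infection at Day 0, with the number at risk per arm.

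**Cost.** SAP wording, one model term and two extra table rows, from data already collected. The added percentages rest on smaller denominators. The extra term matters if events are few, and 9.3 itself foresees that the model may not be run for that reason. If events are sparse, use a penalised fit, or report the adjusted model as a sensitivity analysis.
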